Outcomes	
Primary: total 30d post-discharge home opioid use (number of tablets)
 
Secondary:
 
 
1. Total 7d post-discharge home opioid use
 
2. Total intraoperative non-methadone opioid administration
 
3. Total PACU opioid administration
 
4. Total hospital non-methadone opioid administration
 
 
Exploratory:
 
 
1. Total day of surgery nonmethadone IV opioid administration
 
2. Total day of surgery nonmethadone IV and oral opioid administration
 
3. Total day of surgery opioid administration
 
4. Postoperative day 1 total IV oral and opioid administration (short-stay cohort only)
 
5. Total hospital opioid administration
 
6. PACU pain scores (NRS) and pain relief score; at time-specific intervals
 
7. Duration of intraoperative analgesia (median time to request for re-medication with opioid)
 
8. PACU side effects and adverse events: respiratory depression (4 events occurrence per above), sedation (MOAA/S score), nausea/vomiting (number of events); at time-specific intervals and total
 
9. PACU duration of stay
 
10. 7d and 30d total post-discharge home opioid use (in morphine equivalents)
 
11. 7d and 30d post-discharge pain scores (NRS) and pain relief score; daily
 
12. Total pain relief, calculated as the area under the curve of pain relief score vs time
 
13. 7d and 30d post-discharge opioid side effects (ORSDS); daily, weekly and total (summed and average)
 
14. Time to cessation of post-discharge opioid use
 
15. 7d and 30d post-discharge unused opioid tablet count
 
16. Quality of recovery at 7d, 14d, 21d, 30d, 6 mo, and/or 12 mo (PROMIS global health, PROMIS-29, VR-12, Barthel index, QoR-15, functional independence, return to work)
 
17. Surgeons' opioid prescribing patterns
 

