Intraoperative anesthesia and postoperative analgesia are most commonly achieved with the opioids morphine, hydromorphone, fentanyl, and methadone. Methadone has several therapeutic advantages compared with these other opioids, including more rapid onset, absence of active metabolites, lack of P450 (CYP2B6) genetic influence on the disposition of intravenous methadone, and longer elimination half-life and duration of effect. For example, the elimination half-life of methadone is 1-2 days, compared with remifentanil (0.5 hr), morphine and hydromorphone (2-3 hr), and fentanyl (8-10 hr), although the actual duration of effect of these latter opioids is much shorter due to rapid redistribution. Methadone is both a  $\mu$ -opioid receptor agonist and an N-methyl-D-aspartate (NMDA)-receptor antagonist, which may confer additional therapeutic benefit. In addition, even when given intraoperatively, even in a single dose, methadone, compared with shorter-duration opioids, results in lower pain intensity, better postoperative pain relief, longer duration of analgesia, and, *of particular importance and relevance to the opioid epidemic*, need for fewer postoperative opioid doses, and lower cumulative postoperative opioid use. Moreover, these clinical advantages do not come at a cost of greater opioid side effects (respiratory depression, nausea, vomiting).

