### 2.3. Objective

The overall goal of this research is to improve perioperative pain treatment, decrease post-operative opioid consumption, diminish opioid related side effects, and reduce postop opioid prescribing (and hence opportunity for diversion, abuse, addiction, and fatal overdose). This protocol will test the innovative, paradigm-shifting hypothesis that anesthesia for outpatient surgery with long-duration opioids (methadone), compared with conventional short-duration opioids, achieves better analgesia, with similar or diminished side effects, may reduce development of chronic postsurgical pain, improves recovery, and importantly, decreases postoperative opioid consumption and could hence diminish take-home opioid prescribing and shrink the population reservoir of unused opioids available for diversion and misuse.

Specific Aims: In separate cohorts of patients undergoing moderately painful outpatient surgery (“short-stay”

requiring overnight hospitalization with intended next day discharge and “same-day” surgery), compare the influence of general anesthesia with long-duration vs short-duration opioids on

1. short-term (before discharge) and intermediate term (1-30d post-discharge) opioid consumption.
2. short-term (immediate postoperative), intermediate term (1-30d post-discharge), and chronic (6 and 12 mo) postoperative pain.
3. short-term (immediate postoperative), intermediate term (1-30d post-discharge) opioid-related side effects
4. intermediate (30d post-discharge), and long-term (6 and 12 mo) quality of recovery.

In ambulatory surgery patients, methadone is expected to decrease the need for additional opioids in the immediate postoperative period, decrease 30d opioid consumption, decrease opioid-related side effects, improve postoperative pain relief, decrease the occurrence of chronic postoperative pain, reduce opioid quantities routinely prescribed upon discharge, and improve overall patient recovery

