### 2.6.5 Post-Discharge

Post-discharge care is not altered for purposes of this study. Both groups in both cohorts will receive standard of care post-discharge analgesics as determined by their treating surgeon. These include NSAIDs and opioids (oxycodone, oxycodone+acetaminophen (Percocet, Tylox), hydrocodone+acetaminophen (Norco, Vicodin), tramadol, and codeine+acetaminophen (Tylenol#3)). Selection and quantity of opioids dispensed will be at surgeons' discretion.

Opioids will be dispensed in a medication monitoring system, to measure drug utilization during the 30d post-discharge follow-up period. After discharge, patients record their pain self-assessments, home opioid use, and side effects each day through emailed REDCap or paper surveys, allowing real time data recording. Additional REDCap surveys will be emailed at 6 and 12 mo.

For approximately 30d postop, patients will be queried once daily (evening) regarding pain (average at rest, with activity, with coughing, using NRS), pain relief and pain interference with eight activities of daily living (5-point Likert scale) using the NIH PROMIS Pain Intensity 3A and Pain Interference 6A questionnaires. Recovery is assessed using the QoR-15. Patients also record opioid and non-opioid analgesic use, sedation, and time to return to work and ADLs, and opioid side effects (ORSDS). This electronic-based system has improved daily data capture, improved reliability, and can trigger patient contact if necessary to ensure maximal data capture.

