Postoperative opioid use will be quantified from the medication monitoring system, patients' daily questionnaire, and residual pill counts, and recorded both as the number of tablets used and total morphine equivalents using standard opioid conversion tables.

Recovery from surgery/anesthesia will be assessed at 7d, 14d, 21d, 30d, 6mo and/or 1yr postoperatively, by assessing patient-reported quality of life, functional independence, health status, and ability to return to work and normal activities. We will assess quality of life (Veterans RAND 12-item health survey VR-12, functional independence (Barthel index of activities of daily living, recovery (QoR-15). QoR-15 assesses 5 domains of patient-reported health status: pain, physical comfort, physical independence, psychological support and emotional state using an 11-point numerical rating scale with results summed from 0 (poor recovery) to a maximum of 150 (excellent recovery). These are among the most commonly used instruments, are extensively validated and normed, and are our hospital standards, used locally for several years. Thus we can compare postop with preop metrics, but also with our entire patient database. VR12 is a short form based on the Veterans SF36 version, has 2 domains and 8 dimensions leading to 12 questions, and generates two aggregate summary scores (Physical Component & Mental Component summaries), which are standardized using weights derived from the general population survey and calibrated so that 0.50 is the threshold defining the status of the respondent. Washington University has standing approval ([name]) to use the VR12 and scoring algorithm. The Barthel questionnaire assesses functional independence (able to complete 10 specific normal activities like bathing, feeding, dressing, with any help). It generates a weighted aggregate score 0-100 (100=highest independence). We will evaluate patients' return to employment (defined as work for pay or volunteer work outside home). If applicable, specific questions targeting the reason (pain, addiction, etc) for not returning to work will be asked at 30d, 6mo and 1yr.

Throughout the investigation, any adverse events will be described, recorded and reported according to GCP and IRB regulations.

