### 2.6.8 Primary and secondary outcome measures

Primary outcome measure: Total 30d post-discharge home opioid use (number of tablets). This is because surgeons prescribe a variety of post-op opioids (oxycodone, tramadol, oxycodone+acetaminophen, hydrocodone+acetaminophen, codeine+acetaminophen), we avoid any confounding by use of opioid conversion tables, and the most important factor in opioid diversion and misuse is the number of left-over tablets.

Secondary outcome measures:

1. Total 7d post-discharge home opioid use (number of tablets).
2. Total intraoperative non-methadone opioid administration
3. Total PACU opioid administration
4. Total hospital non-methadone opioid administration

Exploratory outcomes:

1. Total day of surgery nonmethadone IV opioid administration
2. Total day of surgery nonmethadone IV and oral opioid administration
3. Total day of surgery opioid administration
4. Postoperative day 1 total IV oral and opioid administration (for short-stay cohort only)
5. Total hospital opioid administration
6. PACU pain scores (NRS) and pain relief score; at time-specific intervals
7. Duration of intraoperative analgesia (median time to request for re-medication with opioid)
8. PACU side effects and adverse events: respiratory depression (4 events occurrence per above), sedation (MOAA/S score), nausea/vomiting (number of events); at time-specific intervals and total
9. PACU duration of stay
10. 7d and 30d total post-discharge home opioid use (in morphine equivalents)
11. 7d and 30d post-discharge pain scores (NRS) and pain relief score; daily
12. Total pain relief (TOTPAR), calculated as the area under the curve of pain relief score vs time
13. 7d and 30d post-discharge opioid side effects (ORSDS); daily, weekly and total (summed and average)
14. Time to cessation of post-discharge opioid use
15. 7d and 30d post-discharge unused opioid tablet count
16. Quality of recovery at 7d, 14d, 21s, 30d, 6 mo, and/or 12 mo (VR-12, Barthel index, QoR-15, functional independence, return to work)
17. Surgeons' opioid prescribing patterns

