**Aim 3:** Evaluate major and bothersome short-term (before discharge) and intermediate term (1-30d post-discharge) opioid-related side effects with methadone vs short-duration opioids.

Side effects (respiratory-specific events, composite ORSDS) will be compared between the groups using Chi-squared or Fisher exact test, as appropriate, and using logistic models to adjust for important clinical and demographic covariates.

**Aim 4:** Compare overall recovery after surgery/anesthesia with methadone vs short-duration opioids, as defined by changes in reported Health-related Quality of Life, functional independence, and ability to return to work and normal activity.

Overall recovery will be assessed using chi-square tests for categorical outcomes and t-tests for continuous outcomes as well as a repeated measures model to adjust for multiple time points.

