## 5.2 Sources of Materials

The electronic medical record will be used to determine opioid amounts (morphine equivalents) administered during surgery, until discharge, and after discharge, as well as other drugs for treatment and/or prophylaxis of possible opioid side effects. Data collected will include demographics, co-morbidities and diagnoses, vital signs, laboratory results, and medications. Only the research team will have access to individually identifiable patient information, and clinical data will be de-identified after analysis. Data will be collected from medical records by a study team member who has completed appropriate training in HIPAA and clinical research and who is approved by the IRB at Duke University. Data from the electronic ( REDCap) data capture system employed to assess daily drug dosing history, pain, and side effects from after hospital discharge until the postop clinic visit at approximately 30 days will be stored on secure servers. A manual pill count is performed, by subjects and recorded in a REDCap survey. Data are collected from the medication monitoring bottles which provides date/time stamp for pill bottle openings. Subjects will receive emailed REDCap surveys at 6 and 12 months after discharge to inquire about pain, opioid, use, return to work, ADLs, and quality of recovery.

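### QoR-15 is scheduled at discharge and on postoperative days 1-3, but the listed recovery outcome starts at day 7, so early recovery is not a named comparison

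*Combined protocol and SAP*

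**What the plan says.** Five parts of the combined protocol and SAP bear on when recovery is measured and compared.

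- **Outcome list.** Exploratory outcome 16 in section 2.6.8 is "Quality of recovery at 7d, 14d, 21s, 30d, 6 mo, and/or 12 mo (VR-12, Barthel index, QoR-15", followed by functional independence and return to work (21s is evidently a misprint for 21d). The synopsis gives the same times with a longer list of instruments: "Quality of recovery at 7d, 14d, 21d, 30d, 6 mo, and/or 12 mo (PROMIS global health, PROMIS-29, VR-12, Barthel index, QoR-15".
- **Measurements.** Section 2.6.7 repeats the times: "Recovery from surgery/anesthesia will be assessed at 7d, 14d, 21d, 30d, 6mo and/or 1yr postoperatively". It then names VR-12, Barthel and QoR-15.
- **Schedule.** The Patient Surveys/Self-Assessments table ticks QoR-15 at baseline, discharge, daily POD 1-3, and POD 7, 14, 21 and 30. The cells for daily POD 4-30, 6 months and 12 months are blank.
- **Post-discharge text.** Section 2.6.5 says "Recovery is assessed using the QoR-15" in the paragraph on once-daily queries, with no frequency of its own. Section 5.2 says the 6- and 12-month surveys are sent "to inquire about pain, opioid, use, return to work, ADLs, and quality of recovery", without naming an instrument.
- **Aim and analysis.** Section 2.3 states Aim 4 as "intermediate (30d post-discharge), and long-term (6 and 12 mo) quality of recovery". Section 2.8 analyses it with "t-tests for continuous outcomes as well as a repeated measures model to adjust for multiple time points" and does not list the time points.

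**The concern.** The QoR-15 is the only recovery questionnaire that the schedule gives at discharge or on POD 1-3. If its scores at those times belong to no listed outcome, recovery in the first days after surgery has no named comparison, although every patient is asked to provide the data.

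This departs from the plan's own pattern. Aims 1, 2 and 3 each name a short-term period; Aim 4 does not. In-hospital opioid use, PACU pain and PACU side effects have outcomes (exploratory 1-6 and 8), and so do daily pain and ORSDS after discharge (exploratory 11 and 13).

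What is at stake is pre-specification. Because the Aim 4 model does not name its times, one analyst could fit POD 7-30 and another discharge to POD 30, and both would be following the plan. Which model is used, and whether early recovery is reported at all, could then be decided after the data are seen.

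**Working it through.** The plan gives no figure to reproduce here, so the check sets the schedule beside the six times named in outcome 16: days 7, 14, 21 and 30, and 6 and 12 months.

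| Instrument | Scheduled after surgery | Named times matched | Scheduled but not named |
|---|---|---|---|
| VR-12 | POD 7, 14, 21, 30; 6, 12 mo | 6 of 6 | none |
| Barthel | POD 7, 14, 21, 30; 6, 12 mo | 6 of 6 | none |
| QoR-15 | discharge; POD 1, 2, 3, 7, 14, 21, 30 | 4 of 6 | discharge, POD 1, 2, 3 |
| PROMIS Global Health (synopsis list only) | POD 30; 6, 12 mo | 3 of 6 | none |
| PROMIS-29 (synopsis list only) | POD 30 | 1 of 6 | none |

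**Count for QoR-15.** Postoperative assessments: 1 (discharge) + 3 (POD 1-3) + 4 (POD 7, 14, 21, 30) = 8. Outcome 16 covers 4, which leaves 8 - 4 = 4. Short-stay patients are meant to go home the next day, so discharge and POD 1 may be a single assessment. The total is then 7, and 7 - 4 = 3 are outside the outcome.

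**Could a broken table explain this?** The QoR-15 row has all ten cells, and its POD 7-30 ticks line up with those of VR-12 and Barthel. The home diary row does look odd: it is ticked under POD 4-30 and POD 7 but not under POD 1-3, although section 2.6.5 has patients recording every day after discharge. That calls for some caution about the table, but nothing in the QoR-15 row suggests a shift.

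**6 and 12 months.** The times in outcome 16 are joined by and/or, over a pooled set of instruments. PROMIS-29 stands in the synopsis version of that set with one postoperative tick, so the list cannot mean every instrument at every time. For QoR-15 it leaves two readings open, and section 5.2 does not settle which is meant.

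**Daily use.** Section 2.6.5 can be read as daily QoR-15 for about 30 days, whereas the table stops daily QoR-15 after POD 3. These two places also need to be reconciled.

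**The case against.** The strongest reply is that this is a loose list and not a lost analysis. The Aim 4 model names no times, so nothing shuts out the discharge and POD 1-3 scores. A reader might infer that half the QoR-15 data will go unused. The documents do not show that; they show only that no outcome names those scores. This part of the reply stands.

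Three other strong readings also fail.

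- *QoR-15 is promised at 6 and 12 months and then not given.* The and/or wording over a pooled list is not such a promise. The defect is an unclear match of instrument to time.
- *Aim 4 covers only day 30 and later.* Section 2.3 attaches 30 days to its intermediate term, but Aims 1-3 in the same list define that term as days 1 to 30, and section 2.8 states Aim 4 with no time limit.
- *By day 7 the drug has largely gone, so a null result from then on would be uninformative.* Section 2.1 does say "the elimination half-life of methadone is 1-2 days", but drug remaining is not effect on recovery, and nothing in the documents links the two for QoR-15. The trial's hypothesis is that benefit outlasts the drug, down to 30-day opioid use and chronic pain, so a comparison from day 7 is a sensible one.

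It can also be said that early pain and side effects are covered elsewhere and overlap the QoR-15 domains of pain and physical comfort. That is true and narrows the gap. It does not supply a comparison of the composite score, nor of the remaining domains (physical independence, psychological support and emotional state).

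**Conclusion.** The point holds as a gap in the definition of an exploratory outcome. Four of eight postoperative QoR-15 assessments (three of seven if discharge and POD 1 coincide) are in no listed outcome, and early recovery is not a named comparison. Separately, the plan does not make clear whether QoR-15 is meant at 6 and 12 months.

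The conclusion assumes that the QoR-15 row of the table is as the sponsor intended. It assumes nothing about when methadone would affect recovery. The primary outcome, the sample size and the safety assessments are untouched. This is a cheap improvement, not a flaw in the design.

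**What to change.** 1. Add QoR-15 at discharge and on POD 1, 2 and 3 to exploratory outcome 16, in both the synopsis and section 2.6.8, and to the statement of Aim 4. Bring section 2.6.7 into line.
2. In section 2.8, state that the planned repeated-measures model for QoR-15 takes all scheduled postoperative scores, with the baseline QoR-15 as covariate. Say how discharge and POD 1 are handled when they fall together. Baseline adjustment is an analyst's recommendation, not something the text requires. It uses a score already collected. The gain in precision depends on the correlation between baseline and later scores, which the documents do not give, so I put no figure on it.
3. Report the arm difference for POD 1-3 as well as for days 7-30.
4. Give times per instrument. Limit the QoR-15 listing to the scheduled times, and let 6- and 12-month recovery rest on VR-12, Barthel and PROMIS Global Health, which the table does schedule then. Make sections 2.6.5 and 5.2 agree with the table.

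The cost is wording. No visit, questionnaire or patient is added. The downside is one more exploratory comparison in each cohort, since the cohorts are analysed separately; it should be labelled exploratory. The change should be made before unblinding.

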### 2.7 Sample size justification

Sample size is based on the primary outcome measure, total 30d post-discharge home opioid use (number of opioid tablets). Based on available reports (Background) and the Preliminary Results, an ideal state of post-discharge opioid use is defined as  $\leq 5$  pills in 30 days. In the Preliminary data, the rate of "high" post-discharge opioid use (defined as  $> 5$  pills in 30d) was 45% in the short-duration opioid group. With a conservative assumption of a relative risk of 65% for the long-duration group (30% rate of "high" opioid use), a total of 300 subjects (150 per group) will be needed to achieve 80% power assuming alpha = 0.05.

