### 2.8 Hypothesis testing

For all Aims, the two cohorts ("short-stay" and "same-day" surgery) are analyzed separately. Subgroup analysis may also explore specific surgical procedures (procedure-specific analgesia).

Aim 1: Compare the influence of methadone vs short-duration opioids on short-term (before discharge) and intermediate term (1-30d post-discharge) opioid consumption.

30d post-discharge opioid use ( $> 5$  pills) will be compared between arms using Chi-square tests and multiple logistic regression, with opioid group as a predictor and adjusting for the important clinical and demographic covariates. Total pill consumption will be compared using GEE model with Poisson link function. In addition, a time-to-event (survival) model will be fit to compare time to opioid discontinuation between the two groups.

adjusting for the appropriate covariates. Opioid use during intraop, in-hospital post-op, and post-discharge periods will be evaluated using appropriate model and data transformation, depending on the distribution of the data. It is common in some analgesic trials that subjects dropping from different treatment groups differ with respect to reasons for early discontinuation (i.e. not random but outcome-related). Therefore analysis will not be “completers only”. Drop-out rates will be compared between the drug groups, and 30d opioid consumption ( $>5$  vs  $\leq 5$  pills) analyzed with and without drop-outs. Drop-outs will be censored at the time of dropping out in time to discontinuation analysis. A corollary of opioid consumption by patients is opioid prescribing by surgeons. It is possible that surgeons’ prescribing practices (# tablets per patient) may change during the study (coincidentally or as a result thereof) and this will be explored.

**Aim 2:** Compare methadone vs short-duration opioids in reducing short-term (immediate postoperative), intermediate term (1-30d post-discharge), and chronic (6-12 mo) postoperative pain.

Pain reduction effectiveness of methadone vs short-duration opioids will be compared using repeated measures models to adjust for multiple measures on each subject. Depending on the distribution of NRS, VAS and pain relief data, data will be analyzed as normal, or transformed into an ordinal or other scale.

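### The declared primary outcome is a 30-day tablet count, but the 80% power is for the proportion using more than 5 tablets, and no test is named primary

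*Combined protocol and SAP*

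**What the plan says.** The outcome is declared as a count in three places:

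- Synopsis, Outcomes: "Primary: total 30d post-discharge home opioid use (number of tablets".
- Section 2.6.8: "Primary outcome measure: Total 30d post-discharge home opioid use (number of tablets". The reasons given there are that counting tablets avoids opioid conversion tables and that surplus tablets matter most for diversion. No 5-tablet threshold is mentioned.
- Section 2.7, first sentence: "Sample size is based on the primary outcome measure, total 30d post-discharge home opioid use (number of opioid tablets".

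The rest of section 2.7 uses a dichotomy. High use is defined as more than 5 pills in 30 days, with a rate of 45% in the pilot's short-duration group. The effect is set by "With a conservative assumption of a relative risk of 65% for the long-duration group", printed as a 30% rate, and the conclusion is that "a total of 300 subjects (150 per group) will be needed to achieve 80% power assuming alpha = 0.05".

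Under Aim 1 of section 2.8, use of more than 5 pills "will be compared between arms using Chi-square tests and multiple logistic regression, with opioid group as a predictor", with covariate adjustment. The next sentence reads: "Total pill consumption will be compared using GEE model with Poisson link function". The synopsis (Statistical Methodology) lists the same methods. Neither place says which analysis is primary. Section 2.8 also provides for drop-outs: "Drop-out rates will be compared between the drug groups, and 30d opioid consumption", split at 5 pills, is to be analysed with and without them. It does not say which version governs.

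**The concern.** The number of tablets and the share of patients above 5 tablets are different estimands. The first responds to how far above 5 a patient goes; the second does not. The plan credits its sample size and its 80% power to the first, but calculated them for the second.

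The text also points two ways. The outcome declarations lead to the GEE on the count. The power statement and the drop-out analysis lead to the split. If one test is significant in a cohort and the other is not, two readers could each follow the document faithfully and reach opposite primary conclusions. A choice made then, with the results known, would not be credible. The problem arises twice, because the two cohorts are analysed separately.

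**Working it through.** **1. Reproduce the plan's figure.** Inputs from section 2.7: p1 = 0.45, relative risk 0.65, n = 150 per arm, alpha = 0.05. Sidedness is not stated; two-sided is assumed. Let p̄ be the mean of p1 and p2, and d = p1 − p2.

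Power = Φ{[d√n − 1.96 √(2p̄(1−p̄))] / √(p1(1−p1) + p2(1−p2))}

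- p2 = 0.65 × 0.45 = 0.2925, p̄ = 0.37125: (1.929 − 1.96 × 0.6833) / 0.6741 = 0.875, so power is **80.9%**.
- p2 = 0.30 as printed, p̄ = 0.375: (1.837 − 1.96 × 0.6847) / 0.6764 = 0.732, so power is **76.8%**.

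Exact enumeration of the uncorrected chi-square test gives the same two values.

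n per arm for 80% power = [(1.96 √(2p̄(1−p̄)) + 0.8416 √(p1(1−p1) + p2(1−p2))) / d]²

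- p2 = 0.2925: 146.5, so 147 per arm and 294 in total.
- p2 = 0.30: 162.3, so 163 per arm and 326 in total.

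The stated 300 is therefore a two-proportion calculation at the unrounded relative risk. No mean, standard deviation, dispersion or rate ratio for tablets enters it.

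**2. Can power for the count be derived?** No. The documents give no tablet distribution. To show that the 80% does not carry over, assume a negative binomial count with variance m + km², a control mean m1 set so that 45% exceed 5 tablets, and a ratio of means of 0.65, so m2 = 0.65 m1. These are assumptions, not document figures. With v = (1/m1 + k)/150 + (1/m2 + k)/150, power = Φ(|ln 0.65|/√v − 1.96).

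| k | m1 | m2 | √v | Power |
|---|---|---|---|---|
| 1 | 7.03 | 4.57 | 0.1255 | 93% |
| 2 | 9.84 | 6.40 | 0.1685 | 72% |
| 3 | 14.34 | 9.32 | 0.2029 | 56% |

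The same sample size falls on either side of 80%, depending on a distribution the plan does not report.

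**3. Could the two tests disagree?** This too is illustration only: 20,000 simulated trials per setting, 150 per arm, 45% vs 30% above 5 tablets, comparing the uncorrected chi-square test with a log ratio of means using sandwich variance.

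- Negative binomial counts, k from 0.67 to 2.5: the tests disagree in about 18–22% of trials, nearly always with only the count significant. Count power is about 93–98%.
- Assumed alternative in which methadone only moves patients across the cut (5 or fewer: uniform on 0–5; above: 6 plus a lognormal amount with median 12 and log-SD 0.6–1.5; total capped at 60): they disagree in about 21–36%, nearly always with only the split significant. Count power is about 46–61%. The range depends on the cap: about 16–24% at 30 tablets and 23–42% at 90.

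The adjusted logistic regression was not simulated.

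**The case against.** The strongest reply is that the plan does have an answer. It declares the count three times and gives exactly one analysis of total tablets, so the primary outcome maps to the GEE and the split is additional. That reading is fair. It shows the plan to be ambiguous rather than silent. It does not remove the mismatch: on that reading, the power statement and the analysis with and without drop-outs both attach to something that is not a listed outcome.

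The opposite reply is that the split is plainly the intended primary analysis, because it is powered and listed first. A reader might infer this, but the documents do not establish it. The rationale in section 2.6.8 concerns the number of tablets, and the synopsis never mentions a cut at 5.

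It is also fair to say that the disagreement figures come from chosen distributions that point in opposite directions. They show that conflict is possible, not how often it would occur in this trial. The finding does not depend on them.

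**Conclusion.** The point holds from the text alone. The declared primary outcome is a count, the 80% power belongs to an unlisted dichotomy of it, and none of the three candidate analyses is named primary. This must be settled before unblinding because it concerns the primary conclusion in both cohorts.

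For the split, power at 150 per arm is 80.9% at 29.25% and 76.8% at 30%, two-sided testing assumed. For the count, no power can be stated.

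Three stronger readings are not supported:

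- That the trial is underpowered for its declared outcome. The power is unknown and could exceed 80%.
- That 300 per cohort is an arithmetical error. It reproduces at the stated relative risk; only the rounded 30% falls short.
- That the type I error is inflated because either test could count as success. The plan states no such rule, so no such error rate can be attributed to it.

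**What to change.** Before unblinding, make the primary outcome, the power statement and one named two-sided primary test per cohort refer to the same quantity. The choice is the sponsor's.

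**Option 1: keep the tablet count**, in line with the rationale in section 2.6.8. In section 2.8 and the synopsis, name one count test with robust or negative binomial variance as primary. In section 2.7, replace the power statement with one for that test, based on the pilot tablet distribution. Label the analyses of more than 5 tablets supportive. Downside: the restated power may fall below 80%.

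**Option 2: make the split primary.** In the synopsis and section 2.6.8, redefine the primary outcome as the proportion of patients using more than 5 opioid tablets in the 30 days after discharge. In section 2.8 and the synopsis, name the chi-square test as primary, say whether the version with or without drop-outs governs, and label the logistic and count analyses supportive. In section 2.7, remove the reference to the count and give one methadone rate with its power at 150 per arm (29.25%: 80.9%; 30%: 76.8%). Downside: this departs from the declared outcome and its rationale, ignores how far above 5 tablets a patient goes, and requires any registered outcome to be updated.

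Either option costs wording in the synopsis and sections 2.6.8 to 2.8 as needed, plus one restated power figure. Neither changes study procedures or data collection.
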